14.4.2 Clinical Trial Registration

In order to ensure that information on clinical trials reaches the public in a timely manner and to comply with applicable laws, regulations, and guidance, the sponsor will register this clinical trial on ClinicalTrials.gov (and possibly on other publicly accessible websites) before the start of study.

Sponsor contact information, along with the investigator's city, state, country, and recruiting status, will be registered and available for public viewing. Once subjects receive investigator contact information, they may call the site and request enrollment into the trial. The investigative site(s) are encouraged to handle such trial inquiries according to their established subject screening process. If the caller asks additional questions beyond the topic of trial enrollment, they should be referred to the sponsor.

14.4.3 Clinical Trial Results Disclosure

If required at the conclusion of the study, the sponsor will post the results on ClinicalTrials.gov or other publicly accessible websites, as required by applicable national and local laws and/or regulations.

14.5 Insurance and Compensation for Injury

Each subject in the study must be insured in accordance with the regulations applicable to the site where the subject is participating. If a local underwriter is required, then the sponsor or sponsor's designee will obtain clinical study insurance against the risk of injury to clinical study subjects. Refer to the Clinical Study Site Agreement regarding the sponsor's policy on subject compensation and treatment for injury. If the investigator has questions regarding this policy, he or she should contact the sponsor or sponsor's designee.

Appendix A Schedule of Study Procedures

SAD Cohorts 1, 2, 4, 5	Screening	Check-in	Dosing & Observation			Discharge (a)	Outpatient Visit	Early Termination	Follow-up
			Day 1	Day 2	Day 3				
Study Day:	-28 to -2	Day -1	Day 1	Day 2	Day 3	Day 4	Day 8		
Informed consent	X								
Inclusion/exclusion criteria	X	X							
Demographics and medical history	X								
Medication history	X								
Abbreviated Neuro Exam		X	X	X	X	X			
Physical examination	X	X				X	X	X	
Vital signs (c)	X	X	X	X	X	X	X	X	
Weight, height, and BMI (d)	X	X				X	X	X	
Urine drug & cotinine screen	X	X							
Concomitant medications (e)	X	X	X	X	X	X	X	X	X
Concurrent medical conditions	X	X							
Clinical laboratory tests (f)	X	X	X	X	X	X	X	X	
Hepatitis panel and HIV antibody test	X								
FSH (g)	X								
Serum Pregnancy test (hCG)	X								
Urine Pregnancy test		X							
CV Telemetry (n)			X	X					
ECG (h)	X	X	X	X	X	X	X	X	
PGx DNA sample collection (i)			X						
PGx RNA collection (j)			X						
PK blood collection (k)			X	X	X	X		X	
Standardized pre-dose meal (S3 fed cohorts only)			X						

Study drug dosing			X						
PTE assessment (l)	X	X	X						
AE assessment (m)			X	X	X	X	X	X	X

PGx=pharmacogenomic.

- (a) Events listed as occurring at “Inpatient Discharge” visit will occur prior to formal “Inpatient Discharge” but not necessarily at the time of Discharge.
- (b) The Follow-up Visit will occur by telephone on Day 14 (±2) unless abnormal CS findings were observed during previous visits. In these cases, subjects must then be brought back to the clinic for re-evaluation per the investigator’s discretion.
- (c) Vital signs (tympanic body temperature, respiration, pulse, and blood pressure) will be obtained at Screening, Inpatient Check-in (Day -1), Day 1 (pre-dose [within 1 hour and 30 minutes prior to dosing], and at 1, 2, 4-, 6-, 8-, and 12-hours post-dose), and then every 12 hours through 72 hours post-dose, and at Outpatient Visit Day 8, or Early Termination (if applicable) and as appropriate at the Follow-up Visit Day 14 (±2 days). Triplicate orthostatic vital signs (blood pressure and heart rate) will be recorded at baseline (Check-in Day-1) 15 minutes apart.
- (d) Height and BMI will be collected at Screening only.
- (e) Record all ongoing medications from Screening and throughout the study.
- (f) Fasting clinical laboratory tests (hematology, serum chemistry, urinalysis) will be collected at Screening, Day -1, prior to dosing on Day 1, Days 2 through 4, Day 8, Early Termination (if applicable), and as appropriate at the Fasting lipase tests will be collected at Day -1, 24 hours and 48 hours post-dose. An additional tube (for blood serum) will be obtained on Day -1 and Day 2, and the collected serum will be stored at -70C to enable additional, retrospective analyses as needed.
- (g) A FSH level will be obtained on post-menopausal women (defined as continuous amenorrhea of at least 2 years and not surgically sterile).
- (h) Triplicate standard 12-lead ECG will be recorded at Day 1 (pre-dose [within 1 hour prior to dosing], and at 0.5, 1, 2, 4-, 6-, 8-, and 12-hours post-dose), and then every 12 hours until 48 hours post-dose, Day 4, Day 8, Early Termination (if applicable) .
- (i) One blood sample (6 mL) will be collected for pharmacogenomic analysis prior to dosing on Day 1; this will only be collected once per subject.
- (j) 2.5 mL whole blood samples will be collected on Day 1 (pre-dose, 8-, and 24-hours post-dose) for RNA pharmacogenomic analysis. Samples will also be collected during the food effect period.
- (k) Blood samples (6 mL) for PK analyses will be collected at time points indicated in Table 7.
 CSF samples (up to 10 mL) will be collected at 3 h post-dose by lumbar puncture only in selected cohorts as indicated in Table 9.
- (l) PTEs will be collected from signing of informed consent up until dosing on Day 1.
- (m) Any AE with onset or exacerbation after dosing on Day 1 will be captured as an AE.
- (n) CV telemetry should be recorded at least 12 hours prior to dosing, and up to 24 hours after dosing

Cohort 3 SAD Fasted-Fed Crossover	Screening	Dosing and Observation Inpatient					D/C	Inpatient No sooner than +14 days or 4 half-lives of Day 8 visit					+4 days post D/C	E/T	Follow-up Day 14 (±2) (b)
		Days -28 to -2	Day -1	Day 1	Day 2	Day 3		Day 4	Day 8	Day -1	Day 1	Day 2			
Informed consent	X							X							
Inclusion/exclusion criteria	X	X						X							
Admitted to the Clinic		X													
Demographics and medical history	X														
Medication history	X							X							
Abbreviated Neuro Exam		X	X	X	X	X		X	X	X	X	X			
Physical examination	X	X				X	X	X				X	X	X	
Vital signs (c)	X	X	X	X	X	X	X	X	X	X	X	X	X	X	
Weight, height, and BMI (d)	X	X				X	X	X				X	X	X	
Urine drug & cotinine screen	X	X						X							
Concomitant medications (e)	X	X	X	X	X	X	X	X	X	X	X	X	X	X	X
Concurrent medical conditions	X	X						X							
Clinical laboratory tests (f)	X	X	X	X	X	X	X		X	X	X	X	X	X	
Hepatitis panel and HIV antibody test	X														
FSH (g)	X														
Serum Pregnancy test (hCG)	X														
Urine Pregnancy test		X						X							
CV Telemetry (n)			X	X				X	X	X					
ECG (h)	X	X	X	X	X	X	X		X	X	X	X	X	X	
PGx DNA sample collection (i)			X						X						
PGx RNA collection (j)			X						X						
PK blood collection (k)			X	X	X	X			X	X	X	X		X	
Lumbar puncture & CSF collection (k)			X												
Standardized pre-dose meal									X						

Study drug dosing			X						X						
PTE assessment (l)	X	X	X					X	X						
AE assessment (m)			X	X	X	X	X	X	X	X	X	X	X	X	X
Discharged from Clinic						X						X		X	

*S3 Cohort will return no sooner than Day 14 or 4 half-lives (whichever is greater) after Day 8 for the Fed portion. The Fed portion will commence on Day -1 will all the same schedule of events with the exception of **dosing will be post-meal.**

PGx=pharmacogenomic.

- (a) Events listed as occurring at “Inpatient Discharge” visit will occur prior to formal “Inpatient Discharge” but not necessarily at the time of Discharge.
 - (b) The Follow-up Visit will occur by telephone on Day 14 (±2) unless abnormal CS findings were observed during previous visits. In these cases, subjects must then be brought back to the clinic for re-evaluation per the investigator’s discretion.
 - (c) Vital signs (tympanic body temperature, respiration, pulse, and blood pressure) will be obtained at Screening, Inpatient Check-in (Day -1), Day 1 (pre-dose [within 1 hour and 30 minutes prior to dosing], and at 1, 2, 4-, 6-, 8-, and 12-hours post-dose), and then every 12 hours through 72 hours post-dose, and at Outpatient Visit Day 8, or Early Termination (if applicable) and as appropriate at the Follow-up Visit Day 14 (±2 days). Triplicate orthostatic vital signs (blood pressure and heart rate) will be recorded at baseline (Check-in Day-1) 15 minutes apart.
 - (d) Height and BMI will be collected at Screening only.
 - (e) Record all ongoing medications from Screening and throughout the study.
 - (f) Fasting clinical laboratory tests (hematology, serum chemistry, urinalysis) will be collected at Screening, Day -1, prior to dosing on Day 1, Days 2 through 4, Day 8, Early Termination (if applicable), and as appropriate at the Fasting lipase tests will be collected at Day -1, 24 hours and 48 hours post-dose. An additional tube (for blood serum) will be obtained on Day -1 and Day 2, and the collected serum will be stored at -70C to enable additional, retrospective analyses as needed.
 - (g) A FSH level will be obtained on post-menopausal women (defined as continuous amenorrhea of at least 2 years and not surgically sterile).
 - (h) Triplicate standard 12-lead ECG will be recorded at Day 1 (pre-dose [within 1 hour prior to dosing], and at 0.5, 1, 2, 4-, 6-, 8-, and 12-hours post-dose), and then every 12 hours until 48 hours post-dose, Day 4, Day 8, Early Termination (if applicable) .
 - (i) One blood sample (6 mL) will be collected for pharmacogenomic analysis prior to dosing on Day 1; this will only be collected once per subject.
 - (j) 2.5 mL whole blood samples will be collected on Day 1 (pre-dose, 8-, and 24-hours post-dose) for RNA pharmacogenomic analysis. Samples will also be collected during the food effect period.
 - (k) Blood samples (6 mL) for PK analyses will be collected at time points indicated in Table 7.
- CSF samples (up to 10 mL) will be collected at 3 h post-dose by lumbar puncture only in selected cohorts as indicated in Table 9.
- (l) PTEs will be collected from signing of informed consent up until dosing on Day 1.
 - (m) Any AE with onset or exacerbation after dosing on Day 1 will be captured as an AE.
 - (n) CV telemetry should be recorded at least 12 hours prior to dosing, and up to 24 hours after dosing

Multiple-Dose Regimen Cohorts	SCR	Check-in	Inpatient Dosing & Observation							Inpatient Discharge (a)	Outpatient Visit		E/T	Follow-up	
			Day -1	Day 1	Day 2	Day 3	Day 4	Day 5	(model for additional dosing days) Day 6		Day of last dose (e.g. Day7)	1 day after last dose (e.g. Day 8)			2 days after last dose (e.g. Day 9)
Informed consent	X														
Inclusion/exclusion criteria	X	X													
Demographics and medical history	X														
Medication history	X														
Abbreviated neuro exam		X	X						X		X		X	X	
Physical examination	X	X	X						X		X		X	X	
Vital signs (c)	X	X	X	X	X	X	X	X	X	X	X		X	X	
Weight, height, and BMI (d)	X	X	X						X		X		X	X	
Urine drug & cotinine screen	X	X													
Concomitant medications (e)	X	X	X	X	X	X	X	X	X	X	X	X	X	X	X
Concurrent medical conditions	X	X													
Clinical laboratory tests (f)	X	X	X		X		X		X	X	X		X	X	
Hepatitis panel	X														
FSH (g)	X														
Serum Pregnancy test (hCG)	X														
Urine Pregnancy Test		X													
ECG (h)	X	X	X	X	X	X	X	X	X	X	X		X	X	

Multiple-Dose Regimen Cohorts	SCR	Check-in	Inpatient Dosing & Observation							Inpatient Discharge (a)	Outpatient Visit		E/T	Follow-up
			Day 1	Day 2	Day 3	Day 4	Day 5	(model for additional dosing days) Day 6	Day of last dose (e.g. Day7)		1 day after last dose (e.g. Day 8)	2 days after last dose (e.g. Day 9)		
Study Day:	Days -28 to -2	Day -1												
PGx DNA sample collection (i)			X											
PGx RNA collection (j)			X						X					
PK blood collection (k)			X	X	X	X	X	X	X	X	X	X		X
Lumbar puncture & CSF collection (k)									X					
Study drug dosing			X	X	X	X	X	X	X					
PTE assessment (l)	X	X	X											
AE assessment (m)			X	X	X	X	X	X	X	X	X	X	X	X

- PGx=pharmacogenomic (a) Events listed as occurring at “Inpatient Discharge” visit will occur on that day prior to formal “Inpatient Discharge” but not necessarily at the time of Discharge.
- (b) The Follow-up Visit will occur by telephone on Day 21 (± 2) unless abnormal CS findings were observed upon discharge. In these cases, subjects must then be brought back to the clinic for re-evaluation per Investigator’s discretion.
- (c) Vital signs (tympanic body temperature, respiration, pulse, and blood pressure) will be obtained at Screening, Inpatient Check-in (Day -1), Day 1 and Day 7 (pre-dose [within 1 hour and 30 minutes prior to dosing], and at 1, 2, 4-, 6-, 8-, and 12-hours post-dose), Days 2 through 6 (pre-dose and 12 hours post-dose), Day 8, Day 9, Early Termination (if applicable), and as appropriate at the Follow-up Visit Day 14 (± 2 days). Triplicate orthostatic vital signs (blood pressure and heart rate) will be recorded at baseline (Check-in Day-1) 15 minutes apart.
- (d) Height and BMI will be collected at Screening only.
- (e) Record all ongoing medications from Screening and throughout the study.
- (f) Fasting clinical laboratory tests (hematology, serum chemistry, urinalysis) will be collected at Screening, Day -1, prior to dosing on Days 1 through 8, Day 9, Early Termination (if applicable), and as appropriate at the Follow-up Visit Day 21 (± 2 days). Hormone laboratory tests (PRL, thyrotropin [TSH], and FT4) will be collected on Days 1 and 7 (morning [fasting] and 3 hours after dosing), Day 9, and Day 14 under fasted conditions. Fasting lipase tests will be collected at Day -1, Days 2, 7, and 8 (pre-dose). An additional tube (for blood serum) will be obtained on Day -1 and Day 2, and the collected serum will be stored at -70C to enable additional, retrospective analyses as needed.
- (g) A FSH level will be obtained on post-menopausal women (defined as continuous amenorrhea of at least 2 years and not surgically sterile).
- (h) Triplicate standard 12-lead ECG will be recorded at Screening, Inpatient Check-in (Day -1), Days 1 and 7 (pre-dose [within 1 hour prior to dosing], and at 0.5, 1, 2, 4-, 6-, 8-, and 12-hours post-dose), Days 2 through 6 (pre-dose and 12 hours post-dose), Days 8 and 9, Early Termination (if applicable), and as appropriate at the Follow-up Visit Day 21 (± 2 days).
- (i) One blood sample (6 mL) will be collected for pharmacogenomic analysis prior to dosing on Day 1; this will only be collected once per subject.
- (j) 2.5 mL whole blood samples will be collected on Day 1 and Day 7 (pre-dose, 8- and 24-hours post-dose) for RNA pharmacogenomic analysis.
- (k) Blood samples (6 mL) for PK analyses will be collected at time points indicated in Table 8. CSF samples (up to 10 mL) will be collected at 3 h post-dose by lumbar puncture only in cohorts M1 and M2, as indicated in Table 10. Cohort M3 also may, at SRG discretion, undergo PK sampling from CSF, the choice of day and sampling time to be decided by SRG.
- (l) PTEs will be collected from signing of ICF up until dosing on Day 1.
- (m) Any AE with onset or exacerbation after dosing on Day 1 will be captured as an AE.
- (n) 24-hour urine collection is only done for cohort M1, predose and over 24 hours
- (o) If emerging PK data indicate the CVN766 $t_{1/2}$ is 15 hours (or less), the Day 10 visit is not necessary.

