Subjects have a known hypersensitivity to any component of the formulation of CVN766. Subjects have evidence of CS neurologic, cardiovascular, pulmonary, hepatic, hematopoietic disease, renal, metabolic, gastrointestinal, urologic, immunologic, endocrine disease, serious allergy, allergic skin rash, psychiatric disorder, or other abnormality that may impact the ability of the subject to participate or potentially confound the study results. Any finding in the subject's medical history, physical examination, or safety laboratory tests gives reasonable suspicion of a condition that might interfere with the conduct or interpretation of the study.

A complete list of exclusion criteria is provided in Section 7.2.

In addition, subjects may not use any excluded medications (including oral contraceptives as listed in Table 3), supplements, or food products. Concomitant medications and dietary products to be excluded are listed in Table 3.

Main Criteria for Evaluation and Analyses:

- Safety:

Safety parameters will include AEs, clinical laboratory results, vital signs, physical examinations, electrocardiogram (ECG). AEs will be collected from signing the informed consent form (ICF) up until dosing on Day 1 as pretreatment events (PTEs), and any event that occurs from dosing until 14 days after the last dose will be captured as an AE. Vital signs will be recorded at Screening, Inpatient Check-in (Day -1), and throughout the dosing period. Vital signs will include tympanic body temperature measurement, blood pressure, respiration rate, and pulse (beats per minute [bpm]). Triplicate orthostatic vital signs (blood pressure and heart rate) will be recorded at baseline (Check-in Day -1) 15 minutes apart. Heart rate and blood pressure will be measured after at least 5 minutes supine and again at 2 minutes after standing for all scheduled timepoints.

Standard 12-lead ECGs will be recorded at Screening, Inpatient Check-in (Day -1), and periodically throughout the dosing period. Triplicate ECGs will be taken at each timepoint.

A complete list of safety assessments is provided in Section 9.1, and the full Schedule of Study Procedures is provided in Appendix A.

- PK:

The plasma PK parameters are used as PK endpoints to determine drug exposure at each dose and facilitate dose escalations.

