Screening	Inpatient Check-in	Dosing, PK, CSF, & Safety Assessments ^{a,f}	PK / Safety Assessments & inpatient discharge ^b	Follow-Up Visits ^c	Outpatient Follow-Up Call ^d
Day -28 to -2	Day -1	Days 1-7 ^c	1 and 2 days after last dose (e.g. Days 8-9)	3 days ±0 after last dose (e.g. Day 10) & 7 days ± 1 after last dose (e.g. Day 14)	14 days ±2 after last dose (e.g. Day 21)

(a) CSF sampling will occur on Day 7 in cohorts M1 and M2. Cohort M3 also may, at SRG discretion, undergo PK sampling from CSF, the choice of day and sampling time to be decided by SRG.

(b) Discharge from the clinic is planned for Day 9 but may be delayed for additional dosing days or if necessary, to continue monitoring for resolution of AEs.

(c) If emerging PK data indicate the CVN766 $t_{1/2}$ is 15 hours (or less), the visit 3 days after the last dose (e.g., Day 10) may be omitted at Investigator's discretion.

(d) The Follow-up Visit will occur by telephone unless abnormal CS findings are observed upon discharge. In these cases, subjects must return to the clinic for re-evaluation.

(e) Dosing duration may be increased to ≤14 days at the discretion of the SRG based on preliminary PK and projected time to steady-state.

(f) Urine sampling will occur on Day1 and Day 7 in cohort M1.

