9.3.3 Final Visit (discharge day from clinic)

Subjects will be confined to the study clinic for the duration of the treatment period to permit supervised dosing of study drug and repeat study assessments. Subjects participating in the single-dose study and food effect assessment will be discharged no sooner than 72 hours post-dose, and subjects participating in the multiple-dose study will be discharged no sooner than 48 hours following their last dose.

For all subjects receiving study medication, the investigator must complete the End of Study eCRF page.

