9.3.5 Follow-up Visit

The Follow-up Visit will occur by telephone approximately 14 days (± 2) after the final dose of study drug for the SAD cohorts and MAD cohorts unless abnormal CS findings were observed upon discharge or the SRG has determined additional PK sampling timepoints are indicated. In these cases, subjects must then be brought back to the clinic for re-evaluation per the investigator's discretion.

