9.8 Procedures

9.8.1 Collection and Reporting of AEs

9.8.1.1 PTE and AE Collection Period

Collection of PTEs will commence from the time the subject signs the informed consent to participate in the study and continue until the subject is first administered study medication Day 1 or until screen failure. For subjects who discontinue prior to study medication administration, PTEs will be collected for the duration of study participation.

Collection of AEs will commence from the time that the subject is first administered study medication Day 1. Routine collection of AEs will continue until 14 days following last dose.

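### The single-dose closing call (Day 14 ±2) can fall 11 days after dosing and, even on time, is one day short of the 14-day adverse event collection period; it also disagrees with Section 9.3.5

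*Protocol*

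**What the plan says.** The protocol file holds two full copies of the protocol. The text on the closing call and on the adverse event period is the same in both.

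- **Collection period.** Section 9.8.1.1: "Routine collection of AEs will continue until 14 days following last dose". The Study Summary agrees: "any event that occurs from dosing until 14 days after the last dose will be captured as an AE".
- **Single-dose closing call.** Appendix A, note (b) for cohorts 1, 2, 4 and 5 and for the S3 crossover: "The Follow-up Visit will occur by telephone on Day 14" (±2). Table 1 also gives Day 14 ± 2 days.
- **Closing call in the body text.** Section 9.3.5, for single-dose and multiple-dose cohorts alike: "The Follow-up Visit will occur by telephone approximately 14 days" (±2) after the final dose.
- **Multiple-dose closing call.** Appendix A: "The Follow-up Visit will occur by telephone on Day 21" (±2). Table 2 describes the same call as 14 days ±2 after the last dose, with the last dose on Day 7 as the standard case.
- **Day of dosing.** The single dose is given on Day 1, and Appendix A starts adverse event capture there: "Any AE with onset or exacerbation after dosing on Day 1 will be captured as an AE".
- **Endpoint.** Section 5.2.1 lists first the percentage of subjects with at least one treatment-emergent adverse event.

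**The concern.** The closing call is the last column of Appendix A in which adverse events are assessed. If it comes before the end of the stated collection period, nobody is scheduled to ask the subject about the remaining days. For the single-dose cohorts this appears to happen even when the site keeps exactly to the nominal day, because study Day 14 has been used where 14 days after a Day 1 dose was meant.

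Two things are at stake. The first is the primary safety endpoint: an event missed after an early call can only lower the percentage. The second is conduct: a site cannot tell from the protocol whether a single-dose call on Day 12 or on Day 17 is a deviation, because Appendix A and Section 9.3.5 give opposite answers.

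**Working it through.** **Day numbering.** Table 1 has single-dose discharge on Day 4, and Section 9.3.3 (second copy in the file) says these subjects "will be discharged no sooner than 72 hours post-dose". Since 72 hours is 3 days, Day 4 is 3 days after dosing. The multiple-dose PK sampling table agrees: its 24-hour sample is the Day 2 pre-dose sample. So days after last dose = study day − day of last dose, and 14 days after a Day 1 dose is Day 15.

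**Coverage.** Days uncovered = max(0, 14 − days after last dose at the call).

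| Schedule | Call | Study day | Days after last dose | Days uncovered |
|---|---|---|---|---|
| Single dose, Appendix A | earliest | 12 | 12 − 1 = 11 | 3 |
| | nominal | 14 | 14 − 1 = 13 | 1 |
| | latest | 16 | 16 − 1 = 15 | 0 |
| Single dose, Section 9.3.5 | earliest | 13 | 13 − 1 = 12 | 2 |
| | nominal | 15 | 15 − 1 = 14 | 0 |
| | latest | 17 | 17 − 1 = 16 | 0 |
| Multiple dose, 7 days | earliest | 19 | 19 − 7 = 12 | 2 |
| | nominal | 21 | 21 − 7 = 14 | 0 |
| | latest | 23 | 23 − 7 = 16 | 0 |

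The multiple-dose schedule reproduces the 14 days at its nominal day. The single-dose schedule does not. At worst the uncovered share is 3/14 = 21% for single dose and 2/14 = 14% for multiple dose. The two statements of the single-dose window, Days 12 to 16 and Days 13 to 17, overlap without matching.

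**Effect on the percentage.** The protocol gives no expected event rate, so 40% and 20% over 14 days are assumptions. With a constant hazard, and nothing reported after the call, the percentage seen by day d is 1 − (1 − p)^(d/14).

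- All calls at 11 days: 1 − 0.6^(11/14) = 0.33 and 1 − 0.8^(11/14) = 0.16.
- All calls on the nominal Day 14 (13 days): 1 − 0.6^(13/14) = 0.38.
- Calls spread evenly over Days 12 to 16 (also an assumption): mean shortfall (3 + 2 + 1 + 0 + 0)/5 = 1.2 days, and 1 − 0.6^(12.8/14) = 0.37.

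These are upper limits on the loss for each call pattern. Events after a dose cluster early, and some late ones would be volunteered.

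**The case against.** The best reply is that little is likely to be lost. Section 9.8.1.1 keeps collection open to 14 days whatever the call date, and Section 9.8.1.2 lets subjects report events at any time during the study. Observation is close when it matters most, with 72 hours in the unit and a Day 8 visit. The projected half-life in animals is at most 6.5 hours (Section 6.2), so 11 days (264 hours) is about 40 such half-lives, or about 18 at the 15-hour threshold used for the optional multiple-dose visit; the human value is unknown. With 6 active subjects per dose, one subject is 16.7 percentage points, and the study is descriptive. All of this stands, and it limits the size of the point. It does not remove the mismatch, because volunteered reports do not replace a scheduled question.

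One could also say that Section 9.3.5 governs, or that its wording is only approximate. Appendix A would still contradict it, and its own ±2 still permits a call at 12 days.

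A reader might infer more than the documents support:

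- **That every multiple-dose subject called by the target day is short.** An on-target Day 21 call is exactly 14 days after a Day 7 last dose. Only calls at 12 or 13 days fall short.
- **That the S3 fasted period is affected in the same way.** Those subjects return for the fed dose no sooner than 14 days after the first, and Appendix A marks adverse event assessments at that check-in and dosing day. The fed period has no such later contact. The Study Summary adds follow-up at +21 and +28 for S3 but states no starting point, so it cannot be relied on to close the gap.
- **That the unequal follow-up biases a comparison.** Active and placebo subjects in a cohort follow the same blinded schedule. The Study Summary summarises single-dose and multiple-dose cohorts separately, each with its own pooled placebo.

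**Conclusion.** The point holds for S1, S2, S4, S5 and the fed period of S3. The last scheduled adverse event contact is 11 to 15 days after dosing, one day short of the stated period when on time and up to three days short when early. It also conflicts with Section 9.3.5. For the multiple-dose cohorts the shortfall is one or two days and affects only early calls.

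The consequence is a possible slight under-count of the treatment-emergent event percentage. The figures of 33% for a true 40%, and 16% for a true 20%, are a worst case: every call on the earliest day, a constant hazard and no spontaneous reports. They should not be read as an expected bias. With on-time or evenly spread calls, a true 40% falls only to about 37% or 38% even under constant hazard, and early clustering makes the real loss smaller. No conclusion of the study is shown to change. The case for acting is that the protocol contradicts itself on a contact that serves a primary endpoint, and that putting it right costs almost nothing.

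**What to change.** Define the closing call in days after the last dose, in the same words, in Appendix A, Table 1 and Section 9.3.5. Set it no earlier than the end of the 14-day period already stated, for example 14 days after the last dose, -0/+2. That gives Days 15 to 17 for single dose (counted from the fed dose in the S3 fed period) and Days 21 to 23 for 7-day multiple dosing. An anchor on the last dose also keeps working if multiple dosing is extended. Keeping a symmetric ±2 would instead need a nominal single-dose Day 17, since 17 − 2 − 1 = 14.

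The cost is a wording change in three places and a call one to three days later for some subjects. No contact is added.

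This does not settle a separate mismatch. Section 12.1.4.1 counts treatment-emergent events for 30 days (onset − last dose + 1 ≤ 30, so up to 29 days after the last dose), while routine collection stops at 14. Those two periods should be reconciled in the same revision.
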